1.5 Risk/Benefit

While the potential risks are minimal, the findings of this trial may reveal information that can substantially improve medical care for persons with diabetes. Therefore, the overall risk/benefit for patients participating in this trial is assessed as acceptable.

Potential Risks and Discomforts

Trial patients will be informed by the Investigator of the potential risks of ZP4207 and other trial-related procedures before they enter the trial.

In this trial, patients with T1DM will be included to test the safety and efficacy of the BP using either the iLet or the iPhone platform when used with ZP4207 versus Lilly glucagon. The cross-over design with inclusion of 1 group of 10 T1DM patients into the 2 iLet treatment arms and the inclusion of a second group of 10 T1DM patients into the 2 iPhone-based BP treatment arms in a randomized order will allow for a direct comparison of the safety and efficacy of the 2 treatments, based on intra-patient variability only.

Clinical Trial Protocol
ZP4207-16051

Version number: 8.0
Amendment 7.0
Date: 06 January 2017

Patients may experience mild discomfort associated with the insertion of the infusion sets and sensor into the SC tissues. The risk of discomfort due to insertion of infusion sets and sensors is expected to be slightly greater than in their lives outside the trial because more infusion sets will be inserted and a CGM sensor will be inserted. Most patients will use only 1 infusion set and not all will use a CGM sensor in usual care.

There is a potential risk of hypoglycemia, since recombinant insulin analog will be administered. Due to frequent monitoring of glucose and direct supervision by a registered nurse (RN) or Doctor of Medicine (MD) at all times, the risk of a hypoglycemic episodes leading to significant harm to patients is expected to be substantially lower than their risk during their usual therapy.

There is a risk of hyperglycemia. This risk is expected to be less than the risk during the patients' lives outside of the trial based on data from earlier BP trials and the design of this trial.

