3 TRIAL DESCRIPTION

3.1 Summary of Trial Design

This trial is a single-center, open-label, 2-part, randomized cross-over trial. The trial will enroll adult patients with T1DM and will assess the safety and efficacy of the BP using either the iLet or the iPhone platform using the glucagon analog ZP4207 versus Lilly glucagon. In Part 1, up to 10 patients will participate in two 1-day treatment arms in random order (iPhone-based BP using ZP4207 and iPhone-based BP using Lilly glucagon) according to a pre-generated randomization scheme. In Part 2, up to 10 new patients will participate in two 1-day treatment arms in random order (iLet using ZP4207 and iLet using Lilly glucagon) according to a pre-generated randomization scheme. Patients can only participate in 1 part of the trial. An interim database lock may occur upon completion of Part 1 of the trial to analyze the iPhone-based BP data. The iLet and the iPhone-based BP will also administer insulin (insulin lispro, Lilly Humalog) using the same BG control algorithm for all 4 treatment arms. The trial will be conducted at a single center, the MGH Diabetes Center in Boston, MA.

The overall trial design schematic is displayed in [Figure 2](#).

[figure not shown]

Clinical Trial Protocol
ZP4207-16051

[figure not shown]
Version number: 8.0
Amendment 7.0
Date: 06 January 2017

Figure 2. Trial Design Schematic

Part 1:

Part 2:

Patients can only participate in 1 part of the trial.
ADA = anti-drug antibodies; BP = bionic pancreas.

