5 ASSIGNMENT TO TREATMENT GROUPS

This trial is an open-label, 2-part, randomized cross-over trial. Patients who have completed the Screening Visit and meet all of the inclusion and none of exclusion criteria will be enrolled into the trial. In Part 1, up to 10 patients will participate in two 1-day treatment arms in random order (iPhone-based BP using ZP4207 and iPhone-based BP using Lilly glucagon) according to a pre-generated randomization scheme. In Part 2, up to 10 new patients will participate in two 1-day treatment arms in random order (iLet using ZP4207 and iLet using Lilly glucagon)

Clinical Trial Protocol
ZP4207-16051

Version number: 8.0
Amendment 7.0
Date: 06 January 2017

according to a pre-generated randomization scheme. Up to 2 patients may participate in the trial per day. The order of the treatment visits will be randomized in blocks of 2 patients.

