7.4 Treatment Visits (Visit 3 and Visit 4)

- Visit 3 will take place at least 48 hours after screening (Visit 1) and no more than 30 days after screening (Visit 1).
- There will be a 24-hour minimum washout between Visit 3 and Visit 4 and a maximum of 3 weeks between Visit 3 and Visit 4.
- Up to 2 patients may participate per day.
- In Part 1, each patient will participate in 2 treatment visits: 1 with the iPhone-based BP using ZP4207 and 1 with the iPhone-based BP using Lilly glucagon in a randomized order.
- In Part 2, each patient will participate in 2 treatment visits: 1 with the iLet using ZP4207 and 1 with the iLet using Lilly glucagon in a randomized order.
- The night before the treatment visit, patients will place a Dexcom G4 CGM sensor in the abdominal skin and calibrate the sensor when prompted using the provided Nova StatStrip Xpress meter. Patients will be instructed to call if they encounter any difficulty with their CGM.
- Patients will be responsible for their own medications other than insulin during the trial. Any medical advice needed by the patients during their participation that is not directly related to BG control should be obtained from them in their usual manner. Patients may take any over-the-counter medications that they wish during the trial, with the exception of any medication containing acetaminophen as that may cause interference with CGM sensing. If patients experience urgent or emergent medical concerns outside the scope of diabetes care and their primary care physicians, they will be taken to the MGH walk-in clinic or emergency room, or if necessary call 911.
- During the trial, patients will not use any recreational drugs or drugs of abuse. The need to take prescription drugs that dull the sensorium, reduce sensitivity to symptoms of hypoglycemia, or hinder appropriate decision-making may be grounds for exclusion from the trial or discontinuation of participation, a decision that will be made by the Investigator.
- Patients will be instructed concerning diabetes management (e.g., basal insulin rate adjustment by insulin pump) during fasting prior to and between the treatment visits per the medical judgment of the Investigator.
- Patients will not tamper with the BP, including changing any settings.
- Patients may not remove the BP during the trial unless the BP failed or they are withdrawing from the trial.
- The exact time of each procedure and assessment will be documented.

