11 STATISTICS

For all analysis, the 2 treatment arms from Part 1 (iPhone-based BP) will be compared, and the 2 treatment arms from Part 2 (iLet) will be compared. The analysis of Part 1 will be completely separate from the analysis of Part 2.

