11.2.2 Analysis of Efficacy

The analysis of BP function endpoints and glycemic endpoints will be on an intention-to-treat basis. In cases where a treatment arm was not completed (and that arm was not repeated according to protocol criteria), available data from that arm will be used in the data analysis.

The Shapiro-Wilk test will be used to determine the normality of the residuals for each comparison. Summary tables that display descriptive statistics, including percentages, means or medians, and standard deviation and/or ranges, as appropriate, will be provided.

A paired t-test or the Wilcoxon signed rank test for comparison of means with normally or non-normally distributed residuals, respectively, will be used. In a secondary analysis, any period effect and any interaction between treatment and period will be looked for, although no such interaction is predicted for the efficacy outcome. Further details will be included in the SAP.

The number of patients and proportions of severe hypoglycemic events, symptomatic hypoglycemia, and carbohydrate interventions due to hypoglycemia with the event counts will be summarized descriptively, and the proportions will be analyzed by a Fisher's exact test if data allow.

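### Fisher's exact test is named for hypoglycemia and carbohydrate-intervention proportions although both arms of each part are the same patients; a paired exact test should replace it

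*Protocol*

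**What the plan says.** Protocol section 3.1 describes the design: "This trial is a single-center, open-label, 2-part, randomized cross-over trial". Section 5 says that within a part "patients will participate in two 1-day treatment arms in random order", and section 7.4 repeats for both parts that "each patient will participate in 2 treatment visits", one with ZP4207 and one with Lilly glucagon. Section 1.5 gives the reason for this design: the two treatments can be compared "based on intra-patient variability only".

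Section 11 fixes the contrast: "the 2 treatment arms from Part 1 (iPhone-based BP) will be compared, and the 2 treatment arms from Part 2 (iLet) will be compared". It adds: "The analysis of Part 1 will be completely separate from the analysis of Part 2".

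For continuous endpoints, section 11.2.2 names a paired t-test or the Wilcoxon signed rank test. Its last paragraph turns to "The number of patients and proportions of severe hypoglycemic events, symptomatic hypoglycemia, and carbohydrate interventions due to hypoglycemia". These are first summarized descriptively, and then "the proportions will be analyzed by a Fisher's exact test if data allow". The synopsis, under the evaluation of trial data, says the same. Neither place names a paired or cross-over form of the test.

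**The concern.** Fisher's exact test on two proportions treats the rows of the 2x2 table as separate groups of people. Here both rows hold the same people, up to 10 per part, each counted once under ZP4207 and once under Lilly glucagon. The test sees only the two margins. It does not see which patients changed between treatments, and in a cross-over that is where the information on a yes/no outcome lies.

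The protocol is also inconsistent with itself. It justifies the design by within-patient comparison and pairs the continuous endpoints, then drops the pairing for the binary ones without a reason. At stake is whether the p-values printed beside the hypoglycemia and carbohydrate-intervention proportions mean what they appear to mean.

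**Working it through.** The protocol gives no p-value, power or significance level for this comparison, so there is no figure of its own to reproduce.

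**Inputs from the protocol.** Up to 10 patients per part, both treatments in each patient, no pooling of parts (sections 3.1, 5, 7.4 and 11). Section 11.2.4 expects 20 to 24 randomized in all, which is 10 to 12 per part if split evenly.

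**Assumptions not in the protocol.** Two-sided 5% level; a common event rate of 0.5 under the null; within-patient correlation from -1 to 0.5.

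**Notation.** Of n = 10 patients, a have the event on both days, b only on the first-named treatment, c only on the other, d on neither. Fisher uses only a+b and a+c. The exact McNemar test uses only b and c: p = 2 × P(X ≤ min(b,c)), with X binomial(b+c, 0.5).

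**Step 1: same margins, different pairing.**

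- 8/10 versus 2/10. Fisher: 2 × (2025 + 100 + 1)/184756 = 0.023 for every pairing. McNemar: split 6:0, 2/64 = 0.031; split 7:1, 2 × 9/256 = 0.070; split 8:2, 2 × 56/1024 = 0.109.
- 7/10 versus 2/10. Fisher: 2 × 5860/167960 = 0.070 for every pairing. McNemar: split 5:0, 2/32 = 0.063; split 6:1, 2 × 8/128 = 0.125; split 7:2, 2 × 46/512 = 0.180.
- 5/10 versus 0/10. Fisher: 2 × 252/15504 = 0.033. McNemar (split 5:0): 0.0625.

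Fisher's value can therefore be smaller or larger than the paired one, and it does not respond to the pairing.

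**Step 2: all possible results at n = 10.** There are 286 paired tables. The two tests fall on different sides of 0.05 in 12 of them, and in all 12 only Fisher is below. Eight of the 12 have negative within-patient association (ad < bc), for example the 7:1 and 8:2 splits above. The other four are 5:0 splits with 0 or 10 events in one arm. None has positive association.

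**Step 3: actual type I error.** The variance of the difference in proportions is [p1(1−p1) + p2(1−p2) − 2ρ√(p1(1−p1)p2(1−p2))]/n. Fisher in effect sets ρ = 0. A positive ρ makes the true variance smaller than Fisher assumes, and a negative ρ makes it larger. Exact multinomial enumeration at event rate 0.5 gives:

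| Within-patient correlation | Fisher, n = 10 | Exact McNemar, n = 10 | Fisher, n = 12 |
|---|---|---|---|
| −1 | 0.109 | 0.021 | 0.146 |
| −0.3 | 0.029 | 0.016 | 0.047 |
| 0 | 0.013 | 0.009 | 0.023 |
| 0.3 | 0.003 | 0.003 | 0.007 |
| 0.5 | 0.001 | 0.001 | 0.002 |

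At n = 10 with rates 0.7 versus 0.3 and correlation 0.3, power is 0.20 for Fisher and 0.18 for exact McNemar. The paired test gains no power at this size.

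**The case against.** A reader might infer from tables such as 5/10 versus 0/10 that Fisher's test will generally declare too many differences here. The documents do not support that. Section 7.4.1 has the same patient eat the same meal at the same time, do the same structured exercise and, as far as possible, use the same basal rate at both visits. Positive within-patient correlation is then the natural expectation, and there Fisher's error rate is far below 5%. It exceeds 5% only under strong negative correlation. Part of the gap in the 5:0 tables comes from the exact McNemar test itself, which cannot go below 0.0625 with five discordant pairs.

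The comparison also carries little weight. The primary endpoint is safety and tolerability (section 8.1). The hypoglycemia measure named in the objectives is time with CGM glucose below 60 mg/dL (section 2.2), which gets a paired test. The binary outcomes are summarized descriptively first and tested only if the data allow. Section 11 states no significance level or decision rule, and section 11.2.4 says there was no formal sample size calculation.

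All of this stands, and it limits the consequence. It does not make the named test right for the design. Nor is the point merely a detail for the SAP: section 11.2 is a general description, but it names this test. Fisher's test can be used properly in a cross-over, on sequence by direction of change among patients whose two results differ (Mainland-Gart). The protocol instead applies it to the proportions.

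**Conclusion.** The point holds as a mismatch between test and design. An unpaired test is specified for paired yes/no outcomes, its p-value ignores the pairing, and it is inconsistent with the paired tests used elsewhere in section 11.2.2.

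The error has no fixed direction. At zero or positive correlation Fisher is conservative, and exact McNemar is about equally so. For a minority of tables (12 of 286 at n = 10) Fisher falls below 0.05 and the exact paired test does not. These figures rest on an assumed 5% two-sided level, and the error rates also on an event rate of 0.5 and the assumed correlations. Changing the test would alter few conclusions at this sample size; the gain is a p-value that matches the design.

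This should be fixed. It is not critical, because the endpoints are secondary and mainly descriptive and no trial decision is tied to them.

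**What to change.** In section 11.2.2 and in the synopsis, replace Fisher's exact test by the exact McNemar test on patient-level outcomes (at least one event versus none on each treatment day), separately for each part. If period is to be allowed for, name the Mainland-Gart or Prescott test instead. Report the discordant-pair counts and the paired risk difference with its 95% CI.

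Add one sentence on incomplete patients. Section 11.2.2 uses available data from an uncompleted arm, whereas McNemar's test needs both results. State that patients with only one treatment visit stay in the descriptive summaries and do not enter the paired test.

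The cost is two sentences in the protocol, matching text in the SAP and a different SAS procedure. No new data are needed. The change is best made before the interim database lock that section 11.2.3 allows after Part 1.

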11.2.3 Interim Analysis

An interim database lock may occur upon completion of Part 1 of the trial to analyze the iPhone-based BP data.

11.2.4 Sample Size Determination

No formal sample size calculations were made. It is expected that between 20 and 24 patients will be randomized in the trial. The sample size is based on a clinical rather than statistical

Clinical Trial Protocol
ZP4207-16051

Version number: 8.0
Amendment 7.0
Date: 06 January 2017

rationale. The sample size is considered adequate to address the primary trial objective of exploring the safety of ZP4207 when used in the BP and with reference to Lilly glucagon used in the BP.

12 DATA MANAGEMENT AND RECORD KEEPING

Data Management is the responsibility of Medpace. The complete Data Management process will be described in detail and agreed on in the Data Management Plan for this trial.

12.1 Data Handling

Case Report Forms

Electronic Case Report Forms will be used in this trial. The Data Management Department of Medpace will provide the eCRFs. All further information regarding the eCRFs and the data flow will be described and agreed on in the Data Management Plan.

Device-Related Data

During the trial, CGM data, calibration data, insulin dosing data, and glucagon dosing data will be automatically stored in the BP device (from which it will be downloaded at intervals), combined in a single database that will be compared against the primary data files for integrity, and ultimately transferred to Medpace.

12.2 Computer Systems

Data will be processed using a validated computer system conforming to regulatory requirements.

12.3 Data Entry

Data must be recorded using the electronic data capture (EDC) system as the trial is in progress. All site personnel must log into the system using their secure user name and password in order to enter, review, or correct trial data. These procedures must comply with Title 21 of the Code of Federal Regulations (21 CFR Part 11) and other appropriate international regulations. All passwords will be strictly confidential.

12.4 Medical Information Coding

Adverse events and medical history will be coded using the latest version of MedDRA. Prior and concomitant medications will be coded using the World Health Organization Drug Dictionary.

12.5 Data Validation

Validation checks programmed within the EDC system, as well as supplemental validation performed via review of the downloaded data, will be applied to the data in order to ensure accurate, consistent, and reliable data. Data identified as erroneous, or data that are missing, will be referred to the investigative site for resolution through data queries.

The eCRFs must be reviewed and electronically signed by the Investigator.

Clinical Trial Protocol
ZP4207-16051

Version number: 8.0
Amendment 7.0
Date: 06 January 2017

12.6 Record Keeping

Medpace will be responsible for hosting the TMF. Records of patients, source documents, monitoring visit logs, eCRFs, inventory of trial product, regulatory documents, and other Sponsor correspondence pertaining to the trial must be kept in the appropriate trial files at the site. Source data is defined as all information in original records and certified copies of original records of clinical findings, observations, or other activities in a clinical trial necessary for the evaluation and reconstruction of the clinical trial. Source data are contained in source documents (original records or certified copies). These records will be retained in a secure file for the period as set forth in the Clinical Trial Agreement. Prior to transfer or destruction of these records, the Sponsor must be notified in writing and be given the opportunity to further store such records.

13 INVESTIGATOR REQUIREMENTS AND QUALITY CONTROL

13.1 Ethical Conduct of the Trial

The trial will be conducted according to Medpace, MGH, and/or the Sponsor's written instructions (SOPs, working instructions, or process descriptions). Content and definitions of the written instructions are based on the Declaration of Helsinki and the ICH GCP.

13.2 Institutional Review Board

Written favorable opinion must be obtained from the responsible IRB prior to commencement of the trial. Clinical trial submission and reporting requirements before, during, and after completion of the trial will be performed in accordance with national law and local regulations.

All amendments that affect patient safety or the trial integrity (substantial amendments) must not be implemented before favorable opinion has been obtained, unless necessary to eliminate hazards to the patients. Non-substantial amendments do not require favorable opinion by the IRB, but the respective IRB will be notified according to local requirements.

The Sponsor and Investigator must approve any amendment in writing before its implementation.

The Sponsor must maintain an accurate and complete record of all submissions made to the IRB. The records should be filed in the Sponsor's Trial Master File (TMF).

13.3 Informed Consent

In obtaining and documenting informed consent, the Investigator must comply with the applicable regulatory requirement(s) and adhere to the ICH GCP guideline and the requirements in the Declaration of Helsinki.

Prior to any trial-related activity, the Investigator must give the patient oral and written information in a form that the patient can read and understand about all aspects of the trial that are relevant to the patient's decision to participate. The patient will be given ample time to decide whether or not to participate in the trial.

The patient must be informed that his/her personal trial-related data will be used in accordance with the local data protection law. The level of disclosure must also be explained to the patient.

Clinical Trial Protocol
ZP4207-16051

Version number: 8.0
Amendment 7.0
Date: 06 January 2017

The patient must be informed that his/her medical records may be examined by authorized monitors or Clinical Quality Assurance auditors appointed by the Sponsor, by appropriate IRB members, and by inspectors from regulatory authorities.

A voluntary, personally signed and dated ICF must be obtained from the patient prior to any trial-related activity. The ICF must also be signed and dated by the physician or designee who conducted the informed consent procedure. A signed copy of the ICF and any additional patient information must be given to each patient.

The responsibility for taking informed consent must remain with that of a research physician or designee. If information becomes available that may be relevant to the patient's willingness to continue participating in the trial, the Investigator must inform the patient in a timely manner, and a revised written informed consent must be obtained.

Should a protocol amendment become necessary, the ICF may need to be revised to reflect the changes to the protocol. It is the responsibility of the Sponsor to ensure that an amended consent form is reviewed and has received favorable opinion from IRB, and the Investigator must ensure that the amended consent form is signed by all patients subsequently entered into the trial and those currently in the trial, if affected by the amendment.

13.4 Trial Monitoring Requirements

The monitoring procedures for this trial are described in detail in the Monitoring Manual. The objectives of the monitoring procedures are to ensure that (i) the safety and rights of the trial patients are respected, (ii) that accurate, valid, and complete data are collected, and (iii) that the trial is conducted in accordance with the trial protocol, the principles of GCP, and local legislation, including drug accountability.

The monitor must be given direct access to the investigational site files and source documents (original documents, data, and records). Direct access includes permission to examine, analyze, verify, and reproduce any record(s) and report(s) that are important to evaluation of the clinical trial.

Key tasks of the monitor include verifying the presence of informed consent, the adherence to the inclusion/exclusion criteria, the documentation of SAEs, and the recording of all safety and efficacy variables. The monitor will also confirm the completeness of patient records, the adherence to the protocol, ICH GCP, and the progress in patient enrollment and perform drug accountability.

Because no information that could reveal the identity of patients may ever be removed from the trial site, the monitor will visit the site at regular intervals to perform these monitoring tasks. Other contact between the Investigator and monitors will be maintained as required through telephone calls and e-mail. The Investigator and/or key members of staff involved in the trial must be available to assist the monitors during all visits.

Site Initiation Visit

During the Site Initiation Visit (SIV) the CRO, Sponsor, and/or monitors will go through information on the IMP, the protocol, the eCRFs, and other key aspects of the trial with the Investigator and the key members of staff involved in the trial. The topics of the SIV are

Clinical Trial Protocol
ZP4207-16051

Version number: 8.0
Amendment 7.0
Date: 06 January 2017

documented in a SIV report made available to the Investigator. Documentation on the SIV (e.g., power point presentation) should be filed by both Investigator and Sponsor.

